7.4.2. Analysis

Table 14.1.3.1: Demographic data

Continuous parameters: descriptive statistics per treatment group (and overall). Overall p-value to compare all groups: 1-way ANOVA model with factor treatment.

Categorical parameters: frequency tabulation per treatment group (and overall). Overall p-value to compare all groups: Cochran-Mantel-Haenszel test for general association.

Population: safety, ITT, per-protocol.

Table to be created for the Week 12 interim analysis as well, but only for Safety and ITT populations.

Table 14.1.3.2: Demographic data for ACR20 responders versus non-responders at Week 12

Same descriptive table as above, but split up for ACR20 responders and non-responders at Week 12. See further on for the definition of ACR20.

Population: ITT.

Table to be created for the Week 12 interim analysis as well.

Listing 16.2.4.1: Demographic data

Listing per treatment group and per subject of all demographic parameters.

Population: safety.

Table 14.1.3.3: Baseline laboratory data: Tabulation of abnormalities

Frequency tabulation per lab test and per treatment group (and overall) of the baseline result, categorized as low/normal/high according to the normal ranges (see section 12.2.5).

Population: safety.

Table 14.1.3.4: Baseline ECG data: Tabulation of abnormalities

Frequency tabulation per parameter (QT and QTcF) per treatment group (and overall) of the baseline result, categorized as (same as in section 12.3.5):

≤450 ms ;
]450,480] ms ;
]480,500] ms ;
 >500 ms.

Population: safety.

Table 14.1.3.5: Baseline vital signs data: Tabulation of abnormalities

Frequency tabulation per parameter and per treatment group (and overall) of the baseline result, categorized as low/normal/high according to the normal ranges (see section 12.4.3).

Population: safety.

Table 14.1.3.6: Baseline physical examination: Tabulation

Frequency tabulation per eCRF body system and per treatment group (and overall) of the baseline result, categorized as normal/abnormal.

Population: safety.

7.5. BASELINE DISEASE CHARACTERISTICS

7.5.1. Parameters

- Duration of RA (years) = $\frac{(\text{date of initial diagnosis}) - (\text{screening date}) + 1}{365.25}$, rounded to the nearest integer. If the date of initial diagnosis is incomplete, then the following rules will be applied: Missing day: use the first of the month. Missing month: use January.
- Duration of RA, categorized:
 - <0.5;
 - [0.5,2[;
 - [2,5[;

- [5,10[;
- [10,20[;
- ≥20 years
- Screening and baseline CRP
- Screening and baseline CRP, categorized:
 - <0.7 x ULN;
 - [0.7,1.0] x ULN;
 -]1.0,1.2[x ULN;
 - ≥ 1.2 x ULN
- Change in CRP (baseline – screening)
- Screening and baseline TJC68 and SJC66
- Change in TJC68 and SJC66 = baseline – screening
- Screening and baseline DAS28(CRP) – see further sections for the definition of the DAS28(CRP)
- Change in DAS28(CRP) = baseline – screening
- Screening and baseline patient’s global evaluation of disease activity (0-100 mm VAS)
- Change in patient’s global evaluation of disease activity = baseline – screening
- Baseline investigator’s global evaluation of disease activity (0-100 mm VAS)
- Baseline patient’s pain score (0-100 mm VAS)
- Baseline HAQ-DI
- Baseline SDAI
- Baseline CDAI
- RF status, classified as positive/negative based on the upper limit of the normal range (ULN):
 - o Positive: value > ULN
 - o Negative: < value ≤ ULN
 - o Missing: value is missing for any reason.
- Anti-CCP status, classified as positive/negative based on the upper limit of the normal range (ULN):
 - o Positive: value > ULN
 - o Negative: < value ≤ ULN
 - o Missing: value is missing for any reason.
- Affected joints identification
- Prior RA medication:
 - o Generic names, also classified as: biological (anti-TNF or other biological DMARD), anti-TNF, other biological DMARD, conventional DMARD, NSAID, steroid, analgesic, other RA medication.
 - o MTX duration (study screening date – date of start of MTX + 1 day), expressed in years. If there were multiple dosing periods of MTX, then the “duration” will add up all such episodes.
 - o MTX duration, categorized as:
 - <0.5;
 - [0.5,2[;
 - [2,5[;
 - [5,10[;

- [10,20[;
- ≥20 years
- Steroids (as prednisolone-equivalent): total daily dose at the start of the study
- Steroids (as prednisolone-equivalent): total daily dose at the start of the study, categorized as:
 - <5 ;
 - [5,10[;
 - [10,15[;
 - [15,20[;
 - ≥20 mg/day.

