#### **8.3.2 Inclusion Criteria**

To be eligible for study entry subjects must fulfil all of the following criteria:

1. Male or female subjects who are  $\geq 18$  years of age on the day of signing informed consent.
2. Diagnosis of RA since at least 6 months prior to Screening and meeting the 2010 ACR/EULAR criteria of RA and ACR functional class I-III.
3. Have  $\geq 6$  swollen joints (from a 66-joint count) and  $\geq 8$  tender joints (from a 68-joint count) at Screening and Baseline.
4. Screening serum CRP  $\geq 0.7$  x upper limit of the normal (reference) laboratory range (ULN).
5. Have shown an inadequate response in terms of either lack of efficacy or toxicity to MTX.
6. Have agreed to be washed out from MTX for a period of at least 4 weeks before or during the Screening period.
7. If taking oral steroids, these should be at a dose  $\leq 10$  mg/day of prednisone or prednisone equivalent and stable for at least 4 weeks prior to Baseline.
8. If taking non-steroidal anti-inflammatory drugs (NSAIDs), these must be at a stable dose for at least 2 weeks prior to Baseline.
9. The results of the following laboratory tests performed at the central laboratory at Screening must be within the limits specified below:
  - a) Hemoglobin  $\geq 10$  g/dL (International System of Units [SI]:  $\geq 100$  g/L);
  - b) WBCs  $\geq 3.0 \times 10^3$  cells/mm^3 (SI:  $\geq 3.0 \times 10^9$  cells/L);
  - c) Neutrophils  $\geq 2.0 \times 10^3$  cells/mm^3 (SI:  $\geq 2.0 \times 10^9$  cells/L);
  - d) Lymphocytes  $\geq 1.0 \times 10^3$  cells/mm^3 (SI:  $\geq 1.0 \times 10^9$  cells/L);
  - e) Platelets  $\geq 100 \times 10^3$  cells/mm^3 (SI:  $\geq 100 \times 10^9$  cells/L);
  - f) Serum ALT and aspartate aminotransferase (AST)  $\leq 1.5$  x ULN;
  - g) Total bilirubin level  $\leq 1.25$  x ULN;
  - h) Alkaline phosphatase  $\leq 1.5$ ULN;
  - i) Lipase  $\leq 1.5$  x ULN and amylase  $\leq 1.5$  x ULN;
  - j) Creatinine clearance  $>60$  mL/min. Creatinine clearance will be calculated using the Cockcroft-Gault formula.
10. Female subjects must have a negative pregnancy test unless they are surgically sterile or have been post-menopausal for at least one year (12 consecutive months without menses); in case of doubt a determination of serum FSH can be done with FSH levels above 35 mIU/mL being confirmative for menopause.

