### **8.6.1.1 Screening Period (Visit 1, Day -29 to Day -2)**

- Each subject will receive a patient number by using the IXRS system.
- Each subject will be assessed for eligibility against the inclusion and exclusion criteria.
- Subjects taking MTX will be washed out over a 4-week period.
- The subject's full medical history, including concomitant illnesses/diseases and concomitant medications will be documented.
- Demographic data will be recorded.
- Baseline disease characteristics will be recorded.
- A physical examination will be performed, including body weight and height, and the results will be documented.
- Vital signs (blood pressure, heart rate [HR], and oral temperature) will be measured.
- TB test (QuantiFERON-TB Gold test) and chest X-ray will be performed (chest X-ray is to be performed only if not performed in the previous 3 months (results must be available at the site for any chest X-ray performed in the previous 3 months).
- Serology (including hepatitis B and C, HIV 1 and 2, rheumatoid factor [RF] and anti-cyclic citrullinated peptide [CCP] tests) will be performed on a sample collected at this visit.
- A 12-lead ECG will be performed.
- Hematology, clinical chemistry, and urinalysis tests (dipstick and microscopy) will be performed on samples collected at this visit. A serum pregnancy test will be performed on women of childbearing potential.
- Serum CRP will be measured.
- SJC66 and TJC68 evaluations will be performed.
- The subject will complete the Patient's Global Assessment of Disease Activity.

**Note 1: Retesting** during the Screening period is only allowed once for abnormal lab values except for positive QuantiFERON-TB Gold, Hepatitis B, Hepatitis C, HIV or pregnancy test in a female of childbearing potential AND only in case it is still possible to randomize the patient within the per protocol defined Screening period of 28 calendar days.

**Note 2: Rescreening** is only allowed in specific situations and after having obtained written sponsor approval.

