7.5.2. Analysis

Table 14.1.3.7: Screening and baseline disease characteristics

Continuous parameters: descriptive statistics per treatment group (and overall). Overall p-value to compare all groups: ANOVA model with factor treatment.

Categorical parameters: frequency tabulation per treatment group (and overall). Overall p-value to compare all groups: Cochran-Mantel-Haenszel test for general association.

Population: safety, ITT, per-protocol.

Table to be created for the Week 12 interim analysis as well, but only for Safety and ITT populations.

Table 14.1.3.8: Screening and baseline disease characteristics by region

Same descriptive table as above, but split up for the 4 geographical regions.

Population: ITT.

Table to be created for the Week 12 interim analysis as well.

Table 14.1.3.9: Screening and baseline disease characteristics for ACR20 responders versus non-responders at Week 12

Same descriptive table as above, but split up for ACR20 responders and non-responders at Week 12.

Population: ITT.

Table to be created for the Week 12 interim analysis as well.

Table 14.1.3.10: Affected joints: Tabulation

Frequency table of the detailed affected joints, separately for: tender / swollen. No formal comparisons of treatment groups.

Population: Safety.

Table 14.1.3.11: Prior RA medication

Tabulation of the number of prior RA medications (split up for anti-TNF biological DMARD, other biological DMARD, conventional DMARD, NSAID, steroid, analgesic, other RA medication) and the generic terms per treatment group and overall. No formal comparisons of treatment groups.

Population: safety.

Table 14.1.3.12: Prior RA medication for ACR20 responders versus non-responders at Week 12

Same descriptive table as above, but split up for ACR20 responders and non-responders at Week 12. No formal comparisons of treatment groups.

Population: ITT.

Table 14.1.3.13: Prior methotrexate: Descriptive statistics

Descriptive statistics per treatment group (and overall) of the total prior MTX duration (in years).

Frequency per treatment group (and overall) of the total prior MTX duration (in years).

Population: Safety.

Table 14.1.3.14: Prior steroid dose at the start of the study: Descriptive statistics

Descriptive statistics per treatment group (and overall) of the prior steroid dose at the start of the study (mg/day prednisolone-equivalent).

Frequency per treatment group (and overall) of the prior steroid dose at the start of the study.

Population: Safety.

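### The printed MTX duration formula has no stop date, so time off drug counts as exposure when a subject's only MTX episode ended before Screening

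*SAP*

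**What the plan says.** Among the baseline disease characteristics, SAP section 7.5.1 defines "MTX duration (study screening date – date of start of MTX + 1 day), expressed in years". The next sentence adds: "If there were multiple dosing periods of MTX, then the “duration” will add up all such episodes". The result is then put into six classes, with cut points at 0.5, 2, 5, 10 and 20 years. In section 7.5.2, Table 14.1.3.13 summarises total prior MTX duration by treatment group and overall, as descriptive statistics and as frequencies.

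Three places in the protocol determine who can be in that table:

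- Section 8.3.2, criterion 5: "Have shown an inadequate response in terms of either lack of efficacy or toxicity to MTX".
- Section 8.3.2, criterion 6: "Have agreed to be washed out from MTX for a period of at least 4 weeks before or during the Screening period".
- Section 8.6.1.1: "Subjects taking MTX will be washed out over a 4-week period".

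The eligibility criteria set neither a minimum duration of MTX treatment nor a maximum time since the last dose.

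**The concern.** The formula takes the Screening date as the end of MTX treatment. That suits a subject who arrives on MTX and is washed out during Screening. It does not suit a subject who arrives already off MTX, and the protocol provides for such subjects: criterion 6 accepts a washout completed before Screening, criterion 5 accepts toxicity as the form of inadequate response, and section 8.6.1.1 applies the Screening washout only to those taking MTX.

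Inadequate response to MTX defines the study population. Because no entry criterion fixes a minimum exposure, a reader will look to Table 14.1.3.13 to judge how much MTX these subjects had received, and will take total prior MTX duration to mean time on drug. For a single episode the error can only be upward, so any affected subject appears more MTX-experienced than he or she was.

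**Working it through.** The plan gives no worked figure for this variable, so there is nothing to reproduce. The check applies the printed rule to hypothetical dates. The SAP says only that the result is in years; the divisor 365.25 is assumed, taken from the RA duration formula in the same section.

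**One episode.** Let *use* be the days on MTX (stop − start + 1) and *gap* the days from stop to Screening.

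- True duration = use / 365.25
- Printed formula = (Screening − start + 1) / 365.25 = (use + gap) / 365.25
- Excess = gap / 365.25

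The excess does not depend on the length of treatment: 0 days gives 0; 28 days gives 0.077 years; 90 days gives 0.246; 365 days gives 0.999; 730 days gives 1.999. These gaps are assumptions, because the documents give no distribution.

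Whether the class changes depends on where the true value lies:

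| Use (days) | Gap (days) | True (years) | Printed formula (years) | Class |
|---|---|---|---|---|
| 150 | 28 | 150/365.25 = 0.411 | 178/365.25 = 0.487 | unchanged, under 0.5 |
| 170 | 28 | 170/365.25 = 0.465 | 198/365.25 = 0.542 | under 0.5 becomes 0.5 to under 2 |
| 700 | 28 | 700/365.25 = 1.916 | 728/365.25 = 1.993 | unchanged, 0.5 to under 2 |
| 700 | 365 | 700/365.25 = 1.916 | 1065/365.25 = 2.916 | 0.5 to under 2 becomes 2 to under 5 |
| 1800 | 28 | 1800/365.25 = 4.928 | 1828/365.25 = 5.005 | 2 to under 5 becomes 5 to under 10 |

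**Two episodes.** Take two 365-day episodes one year apart, the second ending 365 days before Screening. On a day count from the first dose, the episodes are days 0–364 and 730–1094, and Screening is day 1459. The instruction to add up episodes can be read in three ways:

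- Each episode ends at its own stop date: (365 + 365)/365.25 = 1.999 years. This is correct.
- Only the last episode runs to Screening: (365 + 730)/365.25 = 2.998 years.
- The printed formula is applied to each start date: (1460 + 730)/365.25 = 5.996 years. This exceeds the 1460/365.25 = 3.997 years since MTX was first started, because the final stretch is counted twice.

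**Consistency between subjects.** Suppose the first reading is intended. A second subject who had only the first of those episodes, screened on the same day, follows the printed formula and scores 1460/365.25 = 3.997 years against a true 365/365.25 = 0.999. The subject with twice the exposure is reported at 1.999 years. So even the favourable reading does not make the variable comparable across subjects.

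**Where the variable is used.** MTX duration is not a factor in the logistic model for ACR20 (SAP section 8.1.2). It is also absent from the factors listed for the exploratory stepwise models of ACR20 and of change in DAS28(CRP) (Tables 14.2.1.1.8 and 14.2.1.4.7).

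**The case against.** The strongest reply is that the SAP does not disregard stop dates altogether. Separate dosing periods cannot be told apart, or their lengths added, without knowing when the earlier ones ended. The natural reading of the sentence on multiple periods is therefore start-to-stop lengths, which overstate nothing. This stands. A reader might infer from the formula that exposure is overstated for every subject who stopped before Screening, or that the plan definitely counts overlapping time more than once. The documents support neither inference: the first fails for multi-episode subjects on the natural reading, and the second rests on one of three possible readings.

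A second reply is that long gaps may be rare. Protocol section 6.6 describes subjects with active disease despite MTX treatment, and those on MTX at Screening have no error at all. This stands too, as far as frequency goes. Gaps of years are possible under the criteria, but nothing shows how common they are.

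A third reply is that Table 14.1.3.13 is not the only source on MTX history. Listing 16.2.4.2 gives prior RA medication per subject, though the SAP does not say that it shows dates. MTX duration is also among the section 7.5.1 parameters, so it may appear in the other baseline tables. That is correct: a wrong summary is not the only information available, but it remains wrong.

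None of these replies supplies the missing end date for a single episode.

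**Conclusion.** The point holds for a subject with one MTX episode that ended before Screening. As written, the rule reports time since MTX was started, and the excess over time on drug is exactly the off-drug gap. For subjects with several episodes the text is ambiguous rather than wrong. Subjects on MTX up to Screening are unaffected by the single-episode formula.

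The size per subject is 0.08 years for a 28-day gap and 1.0 year for a 365-day gap, with a change of class only where a boundary is crossed. The effect on the table as a whole cannot be worked out, because the number of affected subjects and their gaps are not stated. It would therefore go too far to say that the population will look materially more MTX-experienced than it was; the documents establish the direction of the error, not its extent.

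The consequence is confined to descriptive reporting: Table 14.1.3.13 and any other baseline table that uses the variable. No efficacy estimate or p-value changes. This is a minor correction. The figures rest on the assumed gaps and on 365.25 days per year.

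**What to change.** Replace the definition in SAP section 7.5.1 with: MTX duration (years) = sum, over non-overlapping MTX episodes, of (min(episode stop date, Screening date) − episode start date + 1) / 365.25. The Screening date then serves as the end date only when MTX is ongoing at Screening. The existing classes can stay and should be applied to this value wherever the variable is tabulated.

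Add a rule for partial MTX start and stop dates. Section 7.5.1 has one for the RA diagnosis date (first of the month, January) but none for MTX, and section 4.4.1 otherwise leaves incomplete dates unimputed. The stop-date convention needs some thought: pairing the earliest possible start with the latest possible stop would lengthen exposure again.

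The cost is a line for the definition, a sentence or two for partial dates, and a small programming change using MTX episode dates from the prior RA medication data. Values for subjects with a single episode ongoing at Screening do not change.

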7.5.2. Analysis

Table 14.1.3.7: Screening and baseline disease characteristics

Continuous parameters: descriptive statistics per treatment group (and overall). Overall p-value to compare all groups: ANOVA model with factor treatment.

Categorical parameters: frequency tabulation per treatment group (and overall). Overall p-value to compare all groups: Cochran-Mantel-Haenszel test for general association.

Population: safety, ITT, per-protocol.

Table to be created for the Week 12 interim analysis as well, but only for Safety and ITT populations.

Table 14.1.3.8: Screening and baseline disease characteristics by region

Same descriptive table as above, but split up for the 4 geographical regions.

Population: ITT.

Table to be created for the Week 12 interim analysis as well.

Table 14.1.3.9: Screening and baseline disease characteristics for ACR20 responders versus non-responders at Week 12

Same descriptive table as above, but split up for ACR20 responders and non-responders at Week 12.

Population: ITT.

Table to be created for the Week 12 interim analysis as well.

Table 14.1.3.10: Affected joints: Tabulation

Frequency table of the detailed affected joints, separately for: tender / swollen. No formal comparisons of treatment groups.

Population: Safety.

Table 14.1.3.11: Prior RA medication

Tabulation of the number of prior RA medications (split up for anti-TNF biological DMARD, other biological DMARD, conventional DMARD, NSAID, steroid, analgesic, other RA medication) and the generic terms per treatment group and overall. No formal comparisons of treatment groups.

Population: safety.

Table 14.1.3.12: Prior RA medication for ACR20 responders versus non-responders at Week 12

Same descriptive table as above, but split up for ACR20 responders and non-responders at Week 12. No formal comparisons of treatment groups.

Population: ITT.

Table 14.1.3.13: Prior methotrexate: Descriptive statistics

Descriptive statistics per treatment group (and overall) of the total prior MTX duration (in years).

Frequency per treatment group (and overall) of the total prior MTX duration (in years).

Population: Safety.

Table 14.1.3.14: Prior steroid dose at the start of the study: Descriptive statistics

Descriptive statistics per treatment group (and overall) of the prior steroid dose at the start of the study (mg/day prednisolone-equivalent).

Frequency per treatment group (and overall) of the prior steroid dose at the start of the study.

Population: Safety.

Listing 16.2.4.2: Prior RA medication

Listing per treatment group and per subject of the prior RA medications.

Population: Safety.

7.6. MEDICAL HISTORY AND CONCURRENT DISEASES**Table 14.1.3.15: Medical history: Tabulation**

Frequency tabulation per treatment group (and overall) of the system organ classes and preferred terms, selecting only the medical history findings (i.e., condition no longer present at the start of the study).

Population: safety.

Table 14.1.3.16: Concurrent diseases: Tabulation

Frequency tabulation per treatment group (and overall) of the system organ classes and preferred terms.

Population: safety.

Listing 16.2.4.3: Medical history

Listing per treatment group and per subject of the medical history data findings (i.e., condition no longer present at the start of the study): original terms as well as coded terms.

Population: safety.

Listing 16.2.4.4: Concomitant diseases

Listing per treatment group and per subject of the concomitant diseases data findings (i.e., condition still present or unknown): original terms as well as coded terms.

Population: safety.

7.7. PRIOR AND CONCOMITANT THERAPIES

Note that prior RA medications are presented in the section on baseline disease characteristics. They are not repeated here.

7.7.1. Classification of Therapies

All prior and concomitant therapies will be allocated into exactly one of the following categories (using the analysis periods as defined in section 3.2):

- Prior only: the therapy ended before the first study treatment administration.
- Concomitant only: the therapy started on or after the first study drug administration.
- Post-treatment: the therapy started after the last study drug administration.
- Prior and concomitant: the therapy started before the first study drug administration, and ended on or after the first study drug administration.

When the start date is completely missing, the therapy is assumed to have started on the same day as the first administration of study medication.

When the end date is missing, the therapy is assumed to be still ongoing after the end of the study.

When the start date is only partially known, the missing parts will be imputed by the first day of the month/year, or the day of the first medication intake in case the nonmissing part matches.

When the end date is only partially known, the missing parts will be imputed by the last day of the month/year, or the day of the last medication intake in case the nonmissing part matches.

Imputation of start and end dates is only done for the classification into prior / concomitant / prior + concomitant. The listing will present the original start and end dates, also when incomplete. Fields like start and stop days will not be derived from imputed incomplete dates.

The relative study day of therapy start and stop will be derived as follows (only listed):

Start day

= (Therapy start date) – (date of first study medication administration) + 1, when the start date of therapy is known and complete, and when the therapy start date is on or after the date of first study medication;

= (Therapy start date) – (date of first study medication administration), when the start date of therapy is known and complete, and when the therapy start date is before the date of first study medication;

= missing when the start date of therapy is unknown, missing, or incomplete.

Stop day

= (Therapy stop date) – (date of first study medication administration) + 1, when the end date of therapy is known and complete, and the end date of therapy is on or after the date of first study medication;

= (Therapy stop date) – (date of first study medication administration), when the end date of therapy is known and complete, and the end date of therapy is before the date of first study medication;

= (Trial termination date) – (date of first study medication administration) + 1, when the therapy is still ongoing when the subject leaves the study; in such cases the stop day will be presented as “>XX days” in the listing;

= missing when the end date of therapy is unknown, missing or incomplete and the therapy isn't ongoing after the subject left the study.

